The study will use a randomized-experimental design and will be randomized via envelope randomization, with experimenters being blinded. A total of 104 patients, 26 in each group, will undergo initial incentive spirometry and force vital capacity (FVC) and FEV₁ tests. Groups will consist of a control versus experimental group, stratified into bilateral and unilateral rib fractures. Three days' worth of data will be collected for each of the tests and will also be collected 24 hours prior to discharge. Length of stays will be compared for experimental and control groups, as well as time to ambulation (collected from the first physical therapy assessment). Injury severity score will also be collected to determine any correlation by severity of injury. Patient satisfaction surveys for the device will also be collected to determine if the patients feel a difference with the device.

4) Background/Scientific Rationale and Significance

Little research as been conducted to determine the significance of a splinting device used in patients with chest trauma, and it is still uncertain whether these devices improve overall patient outcomes. Contradicting studies with similar experimental designs show either some significance (p-value) or insignificance in pulmonary function pre- and post-treatment. This gap in current knowledge leaves room for concern in whether the patient truly benefits from a splinting device in this type of injury. Changes in percent predicted FVC/FEV₁ ratio in this patient population are not readily demonstrated in most of these studies, as well as differing length of stays. This study will contribute to this base of knowledge by determining the effects of the Duracore splinting device on this patient population using the objectives.

5) Inclusion and Exclusion Criteria

Inclusion:

- Adult patient admitted to the trauma service at Penrose Hospital
- Willing and able to comply with all requirements of the study
- Active diagnosis of rib fractures
- Male or female ages 18 and older
- Able to provide written informed consent to participate in the study
- Must be physically able to don and use the splinting device independently without assistance

Exclusion:

- <18 years old
- History of pulmonary disease, lobectomy, or lung transplant
- Current smoker of tobacco products >5 years
- Diagnosis of flail chest

- Pregnant Women
- Prisoners
- Cognitively Impaired; must be alert and oriented x 3

6) Number of Subjects

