Number of subjects was based on a power analysis using FVC/FEV₁ as the primary variable and stratified by unilateral versus bilateral diagnosis. Previous literature suggests a standard deviation of approximately 0.20-0.60 for FVC/FEV₁ values. SD was set at 0.40. Unilateral control was estimated to be 50% of predicted values (FVC/FEV₁) due to the nature of the injury, set at approximately 1.50L, with bilateral set at approximately 1.35L. Unilateral experimental group means were increased by 20% of predicted values to 1.80L, and bilateral to 1.50L. The required sample size to achieve 80% power to detect difference between splint and control groups is 104, with each group requiring 26 subjects each. Power calculations were performed in R version 4.0.0 with the pwr2ppl package, using the anova2x2 function.

Number of subjects to be used are 150 to account for withdrawals, incomplete data sets, extraneous results, etc. This is a single site study.

7) Recruitment Methods

Respiratory Therapy is part of the trauma multi-disciplinary team. and is involved with the care of every trauma patient admitted to Penrose Hospital. During trauma rounds in the ICU and floor patients that met criteria for the study will be identified. The investigators will approach those identified patients for potential enrollment in the study. Note they will not approach any patient for consent that is under their care that shift. There are no flyers or advertisements for this research or device.

8) Study Timelines

It is estimated that it will take at least one year to complete this study to include enrollment, subject completion, and all analysis. All primary variables and analyses should be completed by this time.

9) Study Endpoints

The primary endpoint of this study is to investigate the use of the Duracore splinting device in patients with chest trauma. Hospital length of stays, time to ambulation, a patient satisfaction survey, incentive spirometry, forced vital capacity measurements, and the injury severity score will be correlated to a control group to determine its' effectiveness. The quantitative data points will be collected over the first three days of hospital stay and 24 hours prior to discharge. The qualitative data will be collected prior to patient discharge. The hypothesis of this study is that the use of the Duracore splinting device will reduce hospital length of stays and improve patient lung capacities over the course of admission following chest trauma.

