The design of this study is a randomized experimental trial. The procedures involved in this study will first include obtaining the individual's consent to participate. Incentive spirometry is a standard of care that has been proven to improve deep breathing for patients. FVC/FEV₁ measurements are not always routinely done at this site but has been proven to be an indicator in respiratory deterioration in this population. Enrollment of each subject will be on a one to one basis for control and experimental groups. The trial will be randomized to reduce bias by randomly selecting patients between control and experimental groups by alternating every other patient receiving the treatment. Height, sex, ethnicity, and age will be accounted for as well to calculate the percent predicted FVC/FEV_1 to reduce statistical error. Enrollment will be based on patient consent. After enrollment into the study after admission to the hospital, baseline values of incentive spirometry (IS) and spirometry will be done. The patient will then be placed in the experimental or control group after being assigned a group via envelope randomization. If the patient is under experimental, they will receive a splinting device for treatment. Control groups will receive standard of care treatment without the splinting device. Continued analysis of IS and FVC/FEV₁ will occur over three days, and a final collection prior to discharge. Discharge planning will be coordinated with respiratory therapy, so the patient does not go home without completing the survey and final analysis. The patient satisfaction survey will be a paper survey administered to the patient. Patient identifying information will not be present on this form to maintain confidentiality. The patient will be asked if they would like to complete the form and that it is an anonymous short survey to help with identifying how the patient felt about the research. The subject will only be enrolled in the study for the duration of their hospital stay as an inpatient. There will be no follow-up after discharge, and any patients who are discharged without completing the final analysis will be omitted from the study.

11) Data Analysis Plan

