The primary non-English speaking subject will be Spanish in this region. The hospital has access to translators that can translate for a patient if this were to be necessary. A short form will be used to obtain consent if a non-English speaking patient is enrolled in the study.

Cognitively Impaired Adults/Temporary or Permanent Lack of Capacity to Provide Informed Consent

The process to determine whether an individual can give verbal consent will be conducted by determining if they are oriented to person, place, and time. If this changes after enrollment and the patient is unable to make decisions for themselves, the dedicated medical power of attorney for that patient will be consulted. The use of this device requires intact cognition and may cause them to be omitted from the study in this case.

25) Process to Document Consent in Writing

Informed consent will be obtained in the patient room within the first 24 hours of admission. This will be a paper consent form and will be signed by the subject if the subject decides to be included in the study. All inclusion criteria must be met. The informed consent follows the CIRI template and outlines all procedures and risks associated with the study. Informed consent will be retained for the duration of the study and thereafter in accordance with regulations. Please see the informed consent for all information given to the patient.

26) Drugs or Devices

The splinting device will be primarily made of a urethane coated polyester fabric with anti-microbial additives which is soft, pliable, and stretchable. The device will be stored within the respiratory therapy equipment storage room at Penrose hospital and the research team will be notified by the Trauma team or respiratory therapy when a subject is admitted to the hospital who meets inclusion criteria for the study.

The FDA was contacted regarding the IDE Approval Process. Based on the response from the encounter with the FDA, that during the approval process with the IRB, the governing body of the IRB would deem the device as Significant or Non-Significant. The claim of the Duracore

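### The final lung test is timed one way in sections 3 and 9 and more loosely in section 10, yet patients without it are dropped from the study

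*Combined protocol and SAP*

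**What the plan says.** The timing of the last incentive spirometry (IS) and FVC/FEV₁ test appears in three places.

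- Section 3 (Objectives and Hypothesis(es)): "Three days' worth of data will be collected for each of the tests and will also be collected 24 hours prior to discharge".
- Section 9 (Study Endpoints): "The quantitative data points will be collected over the first three days of hospital stay and 24 hours prior to discharge". The next sentence times the survey differently: "The qualitative data will be collected prior to patient discharge".
- Section 10 (Procedures Involved): "Continued analysis of IS and FVC/FEV₁ will occur over three days, and a final collection prior to discharge".

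Section 10 adds that discharge planning is coordinated with respiratory therapy, "so the patient does not go home without completing the survey and final analysis". It then states the consequence of a missed test: "any patients who are discharged without completing the final analysis will be omitted from the study". Section 13 (Withdrawal of Subjects) lists discharge before the final analysis among the grounds on which a subject may be withdrawn.

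On the start of participation, section 25 says: "Informed consent will be obtained in the patient room within the first 24 hours of admission". Under section 10, baseline testing and group assignment follow consent.

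**The concern.** Section 9 uses one wording for the lung tests and another for the survey, in consecutive sentences. That makes it harder to treat the 24-hour timing as a loose way of saying before the patient goes home. Section 10, which staff would follow at the bedside, uses the looser wording for the lung tests and pairs them with the survey. No section gives a tolerance, and none says what happens when a scheduled daily reading falls in the last day of the stay.

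On its own this would be a missing visit window. The omission rule gives it weight. The rule acts after assignment and depends on discharge, and the hypothesis is that the splint brings discharge forward. A patient removed for want of one spirometry reading also loses a length of stay, a time to ambulation and the daily readings, none of which depend on that test. The comparison is then no longer between the groups as assigned.

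**Working it through.** **The plan's own figure.** Inputs from section 6: control means 1.50 L (unilateral) and 1.35 L (bilateral), splint means 1.80 L and 1.50 L, SD 0.40, 26 per cell. The significance level is not stated; 0.05 two-sided is assumed.

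- Average splint effect: ((1.80 − 1.50) + (1.50 − 1.35)) / 2 = 0.225 L.
- Noncentrality for the splint main effect in a balanced 2×2: N × 0.225² / (4 × 0.40²) = 104 × 0.050625 / 0.64 = 8.23, on 1 and 100 degrees of freedom.
- Power: 81.1% at 26 per cell and 79.5% at 25 per cell.

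The stated 104 is reproduced. The timing question changes none of these inputs, because section 6 ties the 0.225 L to no time point.

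**The three sections side by side.** Which tests meet the stated timing?

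| Test taken before discharge | Sections 3 and 9, read as at 24 hours | Sections 3 and 9, read as within 24 hours | Section 10 |
|---|---|---|---|
| 36 hours | no | no | yes |
| 24 hours | yes | yes | yes |
| 3 hours | no | yes | yes |

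On either reading of sections 3 and 9, some tests that satisfy section 10 do not satisfy them. An exact 24-hour point would also require the discharge time to be known a day ahead.

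**Short stays.** With consent at the latest time that section 25 allows, assignment comes about 24 hours after admission or later. For a 48-hour stay, the point 24 hours before discharge is 48 − 24 = 24 hours after admission, at or before assignment. A reading there could contain no splint time. This applies only if the exact-point reading is meant and consent is late.

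**From timing to analysis set.** Section 10 removes patients who lack the final analysis, and section 13 permits their withdrawal. So whatever staff take the final test to be, including whether a daily reading in the last day counts, helps settle who is analysed.

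**How much loss the plan can absorb.** Enrolment of 150 against 104 leaves 150 − 104 = 46 patients, or 46/150 = 30.7%, for all losses together. The total loss rates below are assumptions, because the documents give none.

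| Assumed total loss | Analysed | Power |
|---|---|---|
| 20% | 120 | 86.3% |
| 30% | 105 | 81.4% |
| 40% | 90 | 75.1% |

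The share of any loss that comes from the final-test rule cannot be derived. The table describes numbers only and does not measure the bias from who is lost.

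**The case against.** The strongest reply is that there is no flat contradiction. A test 24 hours before discharge is also a test before discharge, so section 10 can be read as shorthand. Since the hour of discharge is rarely known a day ahead, a test within the last 24 hours is at least as natural a meaning for sections 3 and 9. On that reading, a patient tested shortly before leaving satisfies all three sections. Section 10 also coordinates discharge so that the test is done first. All of this stands, and it limits the point.

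Three stronger readings are tempting and are not supported.

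- A reader might infer that a completed test becomes invalid if taken at the wrong hour. Sections 10 and 13 act only on patients discharged without the final analysis; neither voids a completed test because of its hour.
- A reader might infer a large loss of power because a test 24 hours before discharge misses the last day of splint use. That needs an assumed pattern of effect growth, an assumed stay, and the final reading as the tested value. The documents give no length of stay and no growth pattern, and section 11 names no time point for the t-test. If the effect does not depend on the last day, the loss is zero.
- A reader might infer that short-notice discharges would take the study below its required number. No rate is given, discharge coordination addresses that case, and a small shortfall would not matter: 102 analysed patients still give 80.3% power under the plan's inputs.

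The reply does not remove the omission rule. However the 24 hours is read, patients are dropped after assignment for lack of one reading.

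**Conclusion.** The point holds in limited form. The sections time the final test differently, with no window and no rule for daily readings, and section 10 attaches removal from the study to its absence. Of the two parts, the omission rule matters more: the wording alone would be a minor clarification, but dropping assigned patients on a discharge-dependent criterion can bias the comparison, including that for length of stay.

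The size cannot be computed from the documents. It depends on how many patients leave without the test and whether they differ between groups, and neither is given. The direction is also unknown. If quick discharges are the ones most often missed, and if the splint shortens stay as hypothesised, short stays would be removed more often from the splint group; both conditions are assumptions. The stated sample size is unaffected. The change is worth making because it is cheap and keeps data that the study will already hold: section 13 retains data already collected unless the subject asks otherwise.

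**What to change.** **1. One definition in sections 3, 9 and 10.** The final reading is the last IS and FVC/FEV₁ test taken after assignment and within the 24 hours before actual discharge, with date and time recorded. A scheduled daily reading in that window counts as the final reading.

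**2. Replace the omission rule.** In section 10, and in the matching withdrawal ground in section 13, state that a patient without this test stays in the analysis in the assigned group, with length of stay, time to ambulation and daily readings kept and only the final reading missing.

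**Cost.** The wording changes in sections 3, 9, 10 and 13, with a protocol amendment for IRB approval, and the CRF needs a time field. No extra tests, staff or patients are needed. The second step is a real change of analysis population and should be presented as such in the amendment. There are two small downsides. For short stays the final reading may be the same test as a daily reading, so the two are not separate values. Some final values will be missing, and the analysis section should say how they are handled.

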Title: Effects of using the Duracore Splinting Device on Patient Outcomes Related to Chest Trauma

Protocol Version Number: 3

Protocol Version Date: 12/8/2020

CHIRB IRBNet ID: 1517921-3

1) Investigators

Principal Investigator

[name] Title: Registered Respiratory Therapist Department: Respiratory Therapy [contact] Email: [contact]

Co-Investigator:

[name] Title: Registered Respiratory Therapist Department: Respiratory Therapy [contact] Email: [contact]

Co-Investigator:

[name] Title: Registered Respiratory Therapist Department: Respiratory Therapy [contact] Email: [contact]

Co-Investigator:

[name] II, M.D. Title: Surgical Trauma Physician Department: Trauma Services Email: [contact]

2) Funding Source

Financial funding was obtained by grants from local agencies through application processes, along with interviews and assessment of the medical device. The first grant was obtained through the Southern Colorado Society of Respiratory Care in hopes to obtain better choices for treatment for patients with rib fractures. Additional funding was provided by the Penrose Foundation as well.

3) Objectives and Hypothesis(es)

The purpose of this study is to use the Duracore patient operated torso splinting device for patients with chest trauma, including rib fractures, to improve deep breathing and help with reduced hospital length of stays (LOS). The hypothesis of this study is that the use of the Duracore splinting device will reduce hospital length of stays and improve patient lung capacities over the course of admission following chest trauma.

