Data analysis will include a two-tailed t-test to account for significance between control and experimental groups. This will be done with both incentive spirometry and FVC/FEV₁. Correlations will be made with time to ambulation and length of stays, as well as injury severity score. Graphic representation of trends will also be used to demonstrate differences between the groups. Qualitative analysis will include providing averages from the questionnaire using a Likert scale. These averages will be used to determine whether the population felt the device provided any help with their chest trauma. Number of subjects was based on a power analysis

using FVC/FEV₁ as the primary variable. Previous literature suggests a standard deviation of approximately 0.20-0.60 for FVC/FEV₁ values. SD was set at 0.40. Unilateral control was estimated to be 50% of predicted values (FVC/FEV₁) due to the nature of the injury, set at approximately 1.50L, with bilateral set at approximately 1.35L. Unilateral experimental group means were increased by 20% of predicted values to 1.80L, and bilateral to 1.50L. The required sample size to achieve 80% power to detect difference between splint and control groups is 104, with each group requiring 26 subjects each. Power calculations were performed in R version 4.0.0 with the pwr2ppl package, using the anova2x2 function. Number of subjects to be used are 150 to account for withdrawals, incomplete data sets, extraneous results, etc. This is a single site study.

Patient satisfaction surveys will use a numbered Likert Scale. The averages of each answer will be used to reinforce the efficacy of the device and correlate to primary data. Randomization will occur by experimenter-blinded envelope randomization.

12) Provisions to Monitor the Data to Ensure the Safety of Subjects

Subjects will be monitored for the duration of their stay by all staff members, and any adverse events related to the device itself will be reported accordingly. This device claims minimal risk to patients due to its unrestrictive and non-invasive nature but will be monitored by investigators for any adverse effects. **The Data Safety Monitoring staff will review all documentation accordingly at least quarterly.**

13) Withdrawal of Subjects

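### The pre-discharge lung reading is timed by length of stay, a hypothesised effect of the splint, so a between-arm t-test on it may understate the lung benefit at equal recovery time.

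*Combined protocol and SAP*

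**What the plan says.** **Timing of the tests.** Section 3 plans three days of spirometry and a further reading that "will also be collected 24 hours prior to discharge". Section 9 repeats the schedule: "The quantitative data points will be collected over the first three days of hospital stay and 24 hours prior to discharge". Section 10 adds a baseline test before allocation, has discharge coordinated with respiratory therapy so that the last test is obtained, and plans no follow-up after discharge.

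**Hypothesis.** Sections 3 and 9 state that the device "will reduce hospital length of stays and improve patient lung capacities over the course of admission following chest trauma". Stay is itself an outcome: "Length of stays will be compared for experimental and control groups" (Section 3). No size is given for the effect on stay.

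**Analysis.** Section 11: "Data analysis will include a two-tailed t-test to account for significance between control and experimental groups", for both incentive spirometry and FVC/FEV₁. It names no time point, no baseline adjustment and no adjustment for day of test. Stay enters this section only as follows: "Correlations will be made with time to ambulation and length of stays, as well as injury severity score".

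**Patients without the last test.** Section 10: "any patients who are discharged without completing the final analysis will be omitted from the study".

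**The concern.** The Day 1 to 3 readings are tied to the calendar of the stay. The last reading is tied to discharge, and the trial hopes to bring discharge forward in one arm only. If that happens while lung volumes are still rising, the two arms are compared at different points of recovery. The two halves of the hypothesis then pull against each other at this reading: the more the splint shortens stay, the smaller the apparent lung benefit there.

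The reading is not peripheral. Discharge is organised around it, patients without it are dropped, and nothing in Section 11 keeps it out of the t-test. A small or reversed difference could be read as evidence that the device does nothing for the lungs.

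**Working it through.** **1. The plan's own figure.** Section 6 gives control means of 1.50 L (unilateral) and 1.35 L (bilateral), splint means of 1.80 L and 1.50 L, SD 0.40 and 26 per cell. Alpha is not stated; two-sided 0.05 is assumed throughout.

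- Average difference = (0.30 + 0.15)/2 = 0.225 L.
- Main effect in the 2×2 ANOVA, 52 per arm: noncentrality = [0.225 / (0.40 × √(2/52))]² = 8.23 on 1 and 100 df, so power is 81.1%. With 25 per cell it is 79.5%. The stated 26 per cell (104 in total) reproduces.

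**2. The same difference under the t-test of Section 11.** An unstratified t-test also carries the spread between strata within each arm. The half-differences between strata are 0.075 L (control) and 0.15 L (splint).

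- Variance = 0.40² + (0.075² + 0.15²)/2 = 0.1741, so SD = 0.417.
- Standard error = 0.417 × √(2/52) = 0.0818 L.
- Power at 0.225 L (102 df) = 77.8%.

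**3. Shift at the pre-discharge reading.** With a constant benefit, a common daily recovery slope and a shorter stay in the splint arm:

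observed difference = 0.225 − (slope × days by which stay is shortened).

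The slope and the number of days are assumptions; the documents give neither. Power below is the chance of a significant result in favour of the splint, using SD 0.417 and 52 per arm.

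| Slope (L/day) | Stay shorter by (days) | Shift (L) | Observed difference (L) | Power |
|---|---|---|---|---|
| any | 0 | 0 | 0.225 | 78% |
| 0 | any | 0 | 0.225 | 78% |
| 0.025 | 0.5 | −0.0125 | 0.2125 | 73% |
| 0.05 | 1 | −0.05 | 0.175 | 56% |
| 0.10 | 1 | −0.10 | 0.125 | 33% |
| 0.15 | 1 | −0.15 | 0.075 | 15% |
| 0.10 | 2 | −0.20 | 0.025 | 5% |
| 0.15 | 2 | −0.30 | −0.075 | below 1% |

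The SD choice matters little. With SD 0.40, power at 0.10 L/day and 1 day falls from 81% to 35%.

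**4. Simulation of how discharge comes about** (assumed slope 0.10 L/day, true benefit 0.225 L unless stated otherwise).

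- Stay 1 day shorter for reasons unrelated to lung volume: 0.127 L before discharge, against 0.227 L on Day 3.
- Same, with no lung effect at all: −0.10 L, so the splint looks harmful.
- No effect on stay: 0.225 L at both times.
- Flat slope: 0.223 L at both times. Falling slope of 0.05 L/day: 0.274 L before discharge, so the shift favours the splint.
- Discharge triggered by reaching a lung-volume threshold: 0.04 L before discharge, against 0.225 L on Day 3. This is one further assumption, as the documents give no discharge criteria.
- Benefit that builds up at 0.05 L/day instead of being constant, stay 1 day shorter: 0.15 L on Day 3 and 0.20 L before discharge. Here the later reading shows more than Day 3, although still less than at equal recovery time.

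**The case against.** **The t-test may never be applied to this reading.** Section 11 names no time point. The pre-discharge value could be tested alone, used as a change from baseline, averaged in, or only plotted with the trends. This stands: a reader might infer that every reading, including the last, will be tested, but the documents do not say so. They also do not rule it out.

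**It is a valid contrast for a different question.** Randomised arms can properly be compared on lung function on leaving hospital. This also stands. The comparison misleads only if it is read as lung function at equal recovery time. Comparing stay between arms would make unequal timing visible, but would not adjust for it.

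**The size is not anchored.** Slope and shortening are both assumed, and the low end of the range costs little (78% to 73%). The 0.225 L is not tied to the discharge reading either. Sections 3 and 6 suggest litres, but Section 4 speaks of a percent predicted ratio; a ratio could have a slope near zero. The point would then rest on incentive spirometry, for which no SD or effect size is given. All of this stands and limits the claim to a conditional one.

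**The early readings would still show a benefit.** Correct, except for patients who leave before Day 3. A reader might infer that shorter stay hides a real lung benefit altogether. The documents do not support that: the problem is confined to one reading, where at 0.05 L/day and 1 day the difference is reduced to 0.175 L rather than lost.

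**Conclusion.** The concern holds as a conditional one. From the text alone, the last lung reading is timed by discharge, earlier discharge is a hypothesised effect of treatment, and the planned t-test takes no account of test time. If stay is shortened and volumes rise during it, the difference at that reading understates the benefit at equal recovery time. The assumed range gives a shift of about −0.01 to −0.30 L against the planned 0.225 L. At 0.10 L/day and 1 day, power falls from about 78% to 33%.

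It would go too far to say that the comparison is biased against a working device. That needs an effect on stay, which is only hypothesised and has no stated size, and a rising slope, which appears nowhere in the documents. The idea that patients go home once they breathe well enough is likewise an assumption; the main argument does not need it.

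The change is worth making because it is cheap and removes a comparison that is hard to interpret. Confidence is medium.

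**What to change.** **Sections 9 and 11.** Make the between-arm tests of incentive spirometry and FVC/FEV₁ at fixed study days (Days 1 to 3), adjusted for the baseline reading. Report the pre-discharge reading descriptively by arm, with the study day of the test (days since admission or enrolment), outside the significance tests. Days since injury would need a new data item, because the variable list in Section 9 has no injury date.

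**Section 10.** Keep patients who lack the pre-discharge reading in the fixed-day comparisons, using all their available Day 1 to 3 values. Otherwise the omission rule carries selection that depends on discharge into the very comparisons meant to avoid it. Bring the matching withdrawal ground in Section 13 into line.

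**Cost.** There is no formal test of lung function at discharge, and a benefit that builds up after Day 3 would be described but not tested. The day of each test must be recorded. The test schedule does not change, and the pre-discharge reading is still collected.

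### Ability to use the splint is required of everyone but no check before assignment is described, so device-linked removals after assignment could fall unevenly on the arms

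*Combined protocol and SAP*

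**What the plan says.** **Eligibility.** Section 5 lists as an inclusion criterion for all candidates: "Must be physically able to don and use the splinting device independently without assistance". Section 7 has suitable patients picked out beforehand: "During trauma rounds in the ICU and floor patients that met criteria for the study will be identified". Section 25, on documenting consent, adds: "All inclusion criteria must be met". None of these sections says how ability to don the splint is judged or recorded.

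**Order of events.** Section 10 puts enrolment and baseline testing first: "After enrollment into the study after admission to the hospital, baseline values of incentive spirometry (IS) and spirometry will be done". Assignment comes next: "The patient will then be placed in the experimental or control group after being assigned a group via envelope randomization". After that, "If the patient is under experimental, they will receive a splinting device for treatment", whereas "Control groups will receive standard of care treatment without the splinting device". No fitting, demonstration or donning test appears before the envelope.

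**Removal after enrolment.** Section 24, on patients who lose orientation after enrolment, has the medical power of attorney consulted and then says: "The use of this device requires intact cognition and may cause them to be omitted from the study in this case". Section 13 lists the withdrawal reasons. They include deterioration of health that prevents participation and discharge before the final assessment, but not inability to don the splint. Section 10 omits patients discharged without the final assessment. Section 13 retains data unless the subject specifies otherwise. Section 11 does not say that patients are analysed as assigned.

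**The concern.** Ability to use the splint is presumed in both arms but put to the test by use in only one. A control patient who could not have managed the device will not be noticed. A similar patient in the splint arm may be noticed at first use and then appears to fail an entry criterion. The plan does not say what happens to that patient's data. Section 24 does give a device-based ground for omission after assignment, and that ground has force only for a splint user.

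If such patients leave the splint arm and their counterparts stay in the control arm, the groups compared are no longer those that were assigned. Patients who cannot manage a torso splint, or who lose orientation, may well have poorer lung volumes, longer stays and later ambulation. Losing them from one arm could then look like a device effect on either half of the hypothesis, lung capacity or length of stay. Section 10 also describes alternating assignment alongside envelopes. If the next arm can be predicted, an unrecorded judgement of ability at entry could also be applied unevenly.

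**Working it through.** **1. The plan's own figure.** Inputs from sections 6 and 11: SD 0.40; control means 1.50 L (unilateral) and 1.35 L (bilateral); splint means 1.80 L and 1.50 L; 26 per cell, 104 in total; 80% power. A two-sided alpha of 0.05 is assumed, because section 11 states a two-tailed test but no alpha.

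- Average splint effect: [(1.80 − 1.50) + (1.50 − 1.35)] / 2 = 0.225 L.
- Standard error with 52 per arm: 0.40 × √(2/52) = 0.0784 L.
- Noncentrality: (0.225 / 0.0784)² ≈ 8.2. With 1 and 100 degrees of freedom, power is 0.811 at 26 per cell. At 25 per cell it is 0.795.

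The stated total of 104 is reproduced. Nothing below alters it.

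**2. Illustration of selective removal.** Suppose a fraction f of the splint arm is removed, and those patients average g SDs below the rest of that arm. The splint-arm mean then rises by f × g × 0.40 L with no device effect. With no true effect, the two-sided rejection rate is Φ(−1.96 + b/SE) + Φ(−1.96 − b/SE), where b is the shift and SE = 0.0784 L. Both f and g are assumptions; the documents give neither.

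| f | g | Shift b (L) | Share of 0.225 L | Type I error |
|---|---|---|---|---|
| 5% | 0.5 | 0.010 | 4.4% | 5.2% |
| 10% | 0.5 | 0.020 | 8.9% | 5.7% |
| 5% | 1.0 | 0.020 | 8.9% | 5.7% |
| 10% | 1.0 | 0.040 | 17.8% | 8.0% |

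Letting the splint arm shrink by the fraction removed changes the last entry only to 7.9%. A more extreme pairing, f = 20% and g = 1.0, shifts the mean by 0.080 L (36% of 0.225 L) and gives 16.1% with the arm so reduced. No such calculation is possible for length of stay or time to ambulation, because the plan gives no SD or expected effect for them.

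**3. What keeping non-users costs.** If a fraction f of the splint arm stays in the analysis and gains nothing, the average effect becomes 0.225 × (1 − f).

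| f | Effect (L) | Power at 104 | Total N for 80% power |
|---|---|---|---|
| 5% | 0.214 | 0.770 | 112 |
| 10% | 0.203 | 0.725 | 128 |
| 20% | 0.180 | 0.623 | 160 |

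Section 6 plans to enrol 150. That covers the first two rows if enough of those patients provide outcome data, but not the third.

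**The case against.** A reader might infer that the criterion filters the splint arm alone, and that both halves of the hypothesis would therefore be biased towards the device. The documents do not support that, for four reasons.

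- The criterion binds every candidate. Sections 7 and 25 place eligibility before the envelope, so on paper it applies equally to both arms. Respiratory therapy is part of the trauma team, and staff could judge ability at the bedside without a splint. A method that is not described is not necessarily absent.
- No section orders removal of a patient found unable to don the splint. Section 13 does not list it, and data are retained by default.
- The section 24 sentence is discretionary, follows consultation of the medical power of attorney, and is not limited to one arm. Cognitive impairment is an exclusion for all patients, and deterioration is a withdrawal reason for all. A control who loses cognition can also be removed.
- The removal rate and the gap in lung volume are assumed. With a 0.5 SD gap and 5% to 10% removed, type I error barely moves.

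All four points stand, and they limit the finding to a risk of unknown size. They do not remove it. The plan still states a ground for omission after assignment that rests on device use, leaves its application to discretion, drops incomplete cases and does not commit to analysing patients as assigned. Retaining data is not the same as analysing them in the assigned group.

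**Conclusion.** The point holds as a gap that leaves room for bias; it does not show that bias is built in. The plan does not say how or when ability to use the splint is verified, use exposes inability in one arm only, and section 24 permits an omission whose reason applies to splint users and not to controls. Removal linked to device use could therefore be unequal and could favour the splint. That direction assumes that those removed do worse than those who stay, which is plausible but not documented.

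The size cannot be derived from the documents. For shifts of 0.01 to 0.04 L, type I error would be about 5.2% to 8%, assuming SD 0.40, 52 per arm, alpha 0.05 and the fractions and gaps shown above. These are illustrations and not estimates. The change is still worth making before enrolment, because control patients who could not have used the splint cannot be identified afterwards.

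**What to change.** 1. **Section 10:** before the envelope is opened, judge and record ability to don and use the splint for every candidate by one stated method. A bedside judgement would do. A demonstration splint is optional, since it would expose control patients to the investigational device, for which section 14 names discomfort and fabric allergy as risks.
2. **Sections 10 and 11:** state that after assignment neither inability to don or use the splint nor lost cognition removes a patient from the analysis in either arm. Analyse all available data by assigned group, subject to consent. This includes length of stay and time to ambulation, which come from the chart and do not depend on completing the final spirometry.
3. **Section 24:** reword the omission sentence so that it does not rest on device use, and reconcile it with the withdrawal rule in section 13. Decisions on capacity and continued participation stay with those sections; the change concerns the analysis only.

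The cost is minor protocol wording and one recorded item per candidate. Keeping non-users in the splint arm may dilute the estimated effect and lower power, as the second table under the working shows. The required total of 104 under the plan's own assumptions does not change.
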